6.3 Subject Exclusion Criteria

- Unmeasurable target tumor site by RECIST 1.1 or PRC (ex: lesions <2 cm on CT or MR scan, leptomeningeal disease, ascites, pleural/pericardial effusion, lymphangitis, non-FDG-avid skin lesions)
- Brain metastases requiring focal or whole brain radiation will be excluded, as these lesions cannot be biopsied and can have life expectancies <6 months.
- Inability to obtain a biopsy of the tumor as deemed by the study Interventional Radiologist
- Prior chemotherapy completed <7 days prior to planned study entry
- Prior RT is allowed and must have been completed more than 7 days before planned study entry.

Note: For re-irradiation cases, standard departmental guidelines should be followed so as to not exceed normal tissue

- Life expectancy less than 6 months
- Intercurrent illness or other major medical condition or comorbid condition that might affect study participation (uncontrolled renal, pulmonary or hepatic dysfunction or infection)
- Renal dysfunction for which cisplatin dose would be considered unsafe.
- Women on study must be neither pregnant nor nursing nor expected to become pregnant during therapy. For premenopausal women, negative pregnancy test within 14 days of RT is required.
- Concurrent active malignancy other than non-melanomatous skin cancer or carcinoma in-situ of the cervix, unless treatment for the previous cancer was completed >2 years prior to study entry and patient has remained disease-free.

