4.1 OVERVIEW OF STUDY DESIGN/INTERVENTION

4.2 Design

This is a single-arm Phase II trial testing the efficacy of concurrent cisplatin and radiation in breast cancer patients with measurable metastatic or locally recurrent tumor, based on HRR status as determined by the MSK-HRR assay. Prior to study enrollment, all patients will require assessment by the radiation oncologist and medical oncologist. Patients will receive a baseline PET-CT +/- MR for evaluation of the tumor to be irradiated and to assess extent of disease systemically. If unavailable within the time specifications of the study, the PET-CT +/- MR will be performed after study registration. Biopsy of the tumor to be irradiated will be performed. Fresh tissue specimens will be sent to the laboratory of [name] for performance of the MSK-HRR Assay. Results from the functional assay will be utilized towards the primary endpoint. Additional unutilized tissue will be sent to the Immune Monitoring Facility Laboratories for TIL analyses to be conducted by [name]. Bloodwork will be sent to the lab of [name] for ctDNA analyses. After the biopsy, patients will undergo simulation for palliative radiation to the tumor site. Following simulation, patient will initiate a 25 mg/m² infusion of cisplatin once a week \pm 3 days. The starting dose will depend on baseline laboratory results within 28 days prior to registration. Following 1-2 weeks of cisplatin, RT will be initiated. Weekly cisplatin (\pm 3 days) will be continued and delivered concurrently with RT. After the completion of RT, weekly cisplatin (\pm 3 days) will be continued until disease progression or until assessment of treatment response at Week 12 post RT (+/- 2 weeks), based on MD discretion. Patients whose HRR status is found to be inevaluable by the MSK assay will not be included in the study and will be replaced by eligible patients.

At Week 12 (12 \pm 2 weeks after RT; with strong recommendation at 12 weeks), repeat imaging with the same imaging methods used for baseline assessment will be performed. Treatment response will be

determined by either PRC or RECIST 1.1.

We estimate accrual will occur at the rate of 15 patients per year. It will take 3.5 years to accrue the total of 54 patients. Patients will be followed up to 24 weeks after completion of RT to determine all study endpoints. Clinical follow-up will continue until death.

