4.3 Intervention

4.3.1 Cisplatin Administration

Cisplatin treatment should be initiated following study registration. The starting dose of cisplatin is established as 25 mg/m² ivpb once a week (\pm 3 days) for 1-2 weeks prior to radiation. Dose modification following the first dose of cisplatin is subject to the discretion of the treating physician. Dosing calculation guidelines will follow MSKCC policies described on the website:

http://mskweb5.mskcc.org/intranet/shared/pharmacy/guidelines/Chemo_Guidelines/Manuals/Cisplatin.html

Cisplatin may be initiated immediately following simulation but prior to first radiation fraction. The rationale is so that the patient may initiate a form of treatment while waiting 1-2 weeks for radiation treatment planning to be completed.

Cisplatin may cause myelosuppression or other known non-hematologic toxicities. Following the completion of RT, pending no toxicities, but prior to the week 12 post RT evaluable timepoint, patients will continue to receive cisplatin based on MD discretion, or until POD.

The starting (first) dose of cisplatin will be 25 mg/m² ivpb once a week (\pm 3 days). Following the first dose of cisplatin, a CBC will be drawn once a week (\pm 3 days) prior to treatment to ensure treatment parameters are met. A comprehensive panel and Mg++ level will be obtained on D15 (\pm 3 days) of every cycle of cisplatin; these values will inform the dose for the following cycle of cisplatin. The length of one cycle of Cisplatin is 21 days. If cisplatin is withheld, the cycle count for treatment is also held. Based on the laboratory values drawn from the prior week's bloodwork, if the following parameters are met, cisplatin should be held as directed.

- If ANC is <1,000 mcL and/or platelets are <100,000 mcL, withhold cisplatin therapy for one week and repeat measurements. Physicians have the option of administering growth factor support during the time when ANC < 1,000 mcL or platelets are < 100,000 mcL. The treating MD may modify the subsequent cisplatin doses at their discretion. If there is a delay of 3 consecutive weeks of treatment due to toxicity, then the patient must discontinue protocol therapy and be removed from the study.
- If the ANC is still <1,000 mcL or platelets are 75,000-99,000 mcL, then hold weekly cisplatin again until the ANC is >1,000 mcL and platelets are >100,000 mcL. The treating MD may modify the subsequent cisplatin doses at their discretion.

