6.1 CRITERIA FOR SUBJECT ELIGIBILITY

6.2 Subject Inclusion Criteria

- Histologically-confirmed invasive triple negative breast cancer (ER <1%, PR <1%, her-2-neu 0-1+ by IHC or FISH-negative) or as determined by MD discretion
- Radiation to the recurrent or metastatic site is clinically indicated and would be considered standard care for palliation or for locoregional control
- Age \geq 18 years
- Tumor to be irradiated is measurable by RECIST 1.1 or PRC (see Appendix 1 and Section 12.0)
- Willingness to undergo tumor biopsy prior to initiation of treatment
- Life expectancy greater than 6 months
- ECOG performance status 0-2
- Any prior chemotherapy is allowed including prior treatment with platinum-containing chemotherapy
- Prior treatment with FDA-approved or investigational biologics or novel molecularly target therapies, including oral or IV formulations, are permitted. Patients must be off prior targeted therapy for at least 14 days prior to study biopsy.

- Use of an effective means of contraception in women of child-bearing potential
- Ability to comprehend and sign informed consent
- Adequate organ and marrow function within 14 days prior to study entry, defined as:
 - Absolute neutrophil count (ANC)>1000/mm³
 - Hemoglobin >9 gm/dl
 - Platelets >100,000/mm³
 - Serum creatinine <1.5 mg/dl OR creatinine clearance of \geq 50 cc/min
 - SGOT/SGPT<2.5X institutional ULN (<5X ULN if known liver metastases)

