8.1 PRETREATMENT EVALUATION

- Within 28 days prior to study registration:

- Evaluation by Radiation Oncology
- Evaluation by Medical Oncology
- PET-CT +/- MR performed at MSKCC
- Complete Blood Count
- Comprehensive Metabolic Panel with Magnesium
- Serum Pregnancy Test for Women of Child Bearing Potential
- Biopsy of target tumor

- After study registration but before cisplatin weekly dose #1:
 - PET-CT +/- MR (only if imaging was not done prior to study registration or not done at MSKCC)
 - Biopsy of target tumor (if not completed prior to registration)
 - Peripheral blood sample for immunologic correlate studies, ctDNA, and/or BRCA mutation status (if unknown prior to study registration).

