10.0 EVALUATION DURING TREATMENT/INTERVENTION

The Table below illustrates the interventions and treatments required at specific time intervals for the study. All evaluations can be performed as frequently as clinically indicated.

Study Requirement	Within 28 days prior to Study Registration	After Study Registration/Before Cisplatin Dose #1	During RT	D1 of Cisplatin Cycle	D8 of Cisplatin Cycle	D15 of Cisplatin Cycle	12+2 weeks after RT	q6 months after RT
Evaluation by Radiation Oncology	X ¹¹		X ¹⁰				X ^{4,11}	X ^{3,4,11}
Evaluation by Medical Oncology ¹¹	X			X ⁸			X ⁴	X ^{3,4}
PET-CT +/- MRI	X	X ¹					X	X ³
Biopsy of Target Tumor	X	X ¹²						
CBC ⁵	X		X	X	X	X	X	X
Mg++, CMP ⁵	X					X		
Pregnancy Test	X							
Peripheral blood sample for immunologic correlate studies, ctDNA, and/or BRCA mutation status		X ²	X ⁹				X	
Cisplatin Administration ⁷			X ⁶	X	X	X		
Toxicity Assessment			X ¹³	X ¹³				

¹ Only if imaging was not done prior to study registration or not performed at MSK

² Obtain only if BRCA 1 or 2 mutation status is unknown at baseline. BRCA 1 or 2 mutation status may also be obtained from the tissue biopsy at baseline. Bloodwork for immune correlates and ctDNA will be obtained at baseline.

³ Recommended but not required.

⁴ May be performed by either radiation oncologist or medical oncologist, but both visits are not required.

⁵ Except at baseline, CBCs will be checked once a week (± 3 days) during cisplatin but prior to administration. Mg2+ and serum chemistries will be obtained on D15 (± 3 days) of every cisplatin cycle.

⁶Radiation will begin following 1-2 weeks of cisplatin. Weekly cisplatin (\pm 3 days) will be continued and delivered concurrently with RT.

⁷ The length of one Cisplatin cycle is 21 days. Cisplatin is administered on D1, D8 and D15 (\pm 3 days) of every cycle. Following the completion of RT, pending no toxicities, but prior to the week 12 post RT evaluable timepoint, patients will continue to receive cisplatin or until POD, based on MD discretion.

⁸ The medical oncologist will evaluate the patient on D1 of each cisplatin cycle. The patient will be assessed for toxicities and will be recorded on a ClinDoc Toxicity form, complete with grade, attribution, start, and stop dates.

⁹ Bloodwork will be obtained during the last week of RT for immune correlates and ctDNA.

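### The pregnancy-test window in 6.3 is tied to RT, not to the cisplatin that starts 1-2 weeks earlier, and most dates allowed for the only scheduled test miss it

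*Combined protocol and SAP*

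**What the plan says.** Section 6.3 (Subject Exclusion Criteria) excludes pregnant and nursing women and adds that for premenopausal women a "negative pregnancy test within 14 days of RT is required".

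Section 8.1 (Pretreatment Evaluation) lists a "Serum Pregnancy Test for Women of Child Bearing Potential" among the items due within 28 days before registration. The section 10 table has one mark in its pregnancy-test row, consistent with that window. No pregnancy test is listed between registration and cisplatin dose 1, or before RT. Section 10 does say: "All evaluations can be performed as frequently as clinically indicated".

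On the order of treatment, section 4.3.1 says: "Cisplatin treatment should be initiated following study registration". Sections 4.2 and 4.3.1 and a footnote to the section 10 table put RT after 1-2 weeks of cisplatin; 4.3.1 explains that the lead covers RT planning. Steps can also fall between registration and cisplatin. Section 8.1 allows, after registration, "Biopsy of target tumor (if not completed prior to registration"), and likewise the baseline PET-CT. Section 4.2 continues: "After the biopsy, patients will undergo simulation for palliative radiation to the tumor site", with cisplatin following simulation.

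**The concern.** A rule on how recent a pregnancy test must be is there to protect the first exposure to a harmful treatment. Here that exposure is cisplatin, yet the 14-day limit counts back from RT. Two problems follow.

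- **The anchor.** A test taken after cisplatin has started can satisfy 6.3, and no recency limit is tied to the cisplatin start.
- **The schedule.** A site that follows 8.1 and the section 10 table exactly can register a woman whose only test is too old for 6.3 by the time RT begins. Section 15.2 has staff confirm eligibility at registration, when the RT start date that decides this criterion still lies ahead.

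At stake are fetal exposure to cisplatin on the strength of an old test, and avoidable protocol deviations or unscheduled tests.

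**Working it through.** The plan gives no figure to reproduce, so the check is a count of calendar days.

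**Inputs**

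- t = days from the test to registration, 0 to 28, which gives 29 permitted dates (8.1).
- L = days from first cisplatin to RT, 7 to 14 (4.2, 4.3.1, section 10 footnote).
- g = days from registration to first cisplatin. The documents set no value, so g is assumed and varied.
- 6.3 is read as 14 days counted back from the start of RT.

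**1. Where the 6.3 window lies relative to cisplatin dose 1**

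The window runs from day L − 14 to day L, with dose 1 on day 0.

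- L = 7: day −7 to day +7. Share on or after dose 1: 7/14 = 50%.
- L = 14: day 0 to day +14. Share: 14/14 = 100%, apart from a test on the day of dose 1 before the infusion.

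**2. Age of the scheduled test at RT**

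Age = t + g + L. With g = 0:

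- L = 7: 0 + 7 = 7 to 28 + 7 = 35 days.
- L = 14: 0 + 14 = 14 to 28 + 14 = 42 days.

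The limit is 14 days.

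**3. Permitted dates that meet 6.3**

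The rule is met when t + g + L ≤ 14, that is t ≤ 14 − L − g. The number of qualifying dates is max(0, 15 − L − g) out of 29.

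| Gap g (assumed) | L = 7 | L = 10 | L = 14 |
|---|---|---|---|
| 0 days | 8 (28%) | 5 (17%) | 1 (3%) |
| 3 days | 5 (17%) | 2 (7%) | 0 |
| 7 days | 1 (3%) | 0 | 0 |
| 8 or more days | 0 | 0 | 0 |

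As a sensitivity check, shortening the 1-week lead by the 3-day dosing tolerance (L = 4, g = 0) gives 15 − 4 = 11 qualifying dates. The other 18 of 29 (62%) still miss.

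**4. Age of the scheduled test at first cisplatin**

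Age = t + g: 0-28 days with no gap, 7-35 days with a 7-day gap.

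**5. Effect of moving the anchor alone**

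With a limit of 14 days before dose 1, a date qualifies when t + g ≤ 14. That is 15 of 29 dates at g = 0 and 15 − 7 = 8 of 29 at g = 7. Rewording 6.3 is therefore not enough; the 28-day window must change too.

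**The case against.** The strongest reply is that the two rules are cumulative. Section 8.1 secures a serum test before any study drug, 6.3 asks for a second, recent test for RT, and a patient can meet both. The exclusion of pregnant women and the contraception requirement in 6.2 do not depend on the window. Section 10 permits extra tests, and the eligibility checklist in 15.2 should bring 6.3 to the site's attention. This stands in part: there is always a test before cisplatin, and the other safeguards reduce the risk. But that test has no 14-day limit, the RT-linked test is not in the schedule, and permission to repeat a test does not prompt one. A checklist signed at registration can flag the RT-linked rule, but cannot confirm it while the RT date lies ahead.

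A second reply is that dates are not patients. Section 6.2 requires "Adequate organ and marrow function within 14 days prior to study entry". If the pregnancy test is drawn with those bloods (an assumption), t is 0-14, and with no gap and a 7-day lead 8 of 15 dates (53%) qualify. This is fair. The counts do not show how often patients would miss 6.3, and in that one case most dates pass. With the same draw, a one-day gap leaves 7 of 15 (47%), and a 14-day lead with no gap leaves 1 of 15.

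Third, the gaps are assumed, and no document fixes how recent a test before cisplatin must be. Both are true. The no-gap column needs no assumed delay, and the exact interval is for the sponsor to set.

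**Conclusion.** The concern holds. The recency rule in 6.3 is anchored to the second treatment, and no stated rule ensures a recent test before the first. For every lead of 7-14 days, at least 21 of the 29 permitted test dates (72%) fall outside the 6.3 window even with no gap, and 28 of 29 (97%) do so with a 14-day lead. This rests on counting from the start of RT and weighting the permitted dates equally. The documents do not give the number of premenopausal participants or the actual timing of tests, so the number of patients affected cannot be stated. The likely consequence is a deviation or an unscheduled test, possibly after cisplatin has begun. The sample size, power and primary analysis are unaffected. The change should be made because the misdirected rule concerns safety and is cheap to correct.

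**What to change.** - **6.3:** tie the requirement to first study treatment, for example a negative test within 14 days before cisplatin dose 1. The sponsor sets the interval; 6.2 already uses 14 days for organ and marrow function, counted from study entry.
- **8.1 and the section 10 table:** match this, either by shortening the 28-day window for this test or by moving the test to the column between registration and first cisplatin. If the window is shortened but still counted from registration, add a repeat for cases where a delay before cisplatin makes the test too old.
- **Pre-RT repeat:** keep one only if the sponsor wants it, and then show it in the table.
- **Population:** use one term in both places; 6.3 refers to premenopausal women and 8.1 to child-bearing potential.

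The cost is wording in three places and a tighter window on a test already being done, with an occasional repeat serum test.

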7.0 RECRUITMENT PLAN

Potential research subjects will be identified by either a breast medical oncologist, breast surgeon or breast radiation oncologist at MSKCC. Eligible patients include women with breast cancer with measurable disease requiring radiation treatment. These include locoregionally progressive or recurrent disease in the breast/chest wall and/or regional lymph nodes, or sites of metastatic disease requiring local palliative treatment. The patients will be referred to the Department of Radiation Oncology, where informed consent will be obtained. This study is open to recruitment all Regional sites, however biopsies of the target tumor for the study must be performed at the Main Campus.

MSKCC has filed forms HHS 441, 641 and 639-A. We have taken notice of NIH/ADAMHA policies concerning the inclusion of women and minorities in clinical research populations. We expect that the study population will be fully representative of the range of patients seen at MSKCC without exclusion to age (≥ 18 years) or ethnic background.

Potential research subjects will be identified by a member of the patient's treatment team, the protocol investigator, or research team at Memorial Sloan-Kettering Cancer Center (MSKCC). If the investigator is a member of the treatment team, s/he will screen their patient's medical records for suitable research study participants and discuss the study and their potential for enrolling in the research study. Potential subjects contacted by their treating physician will be referred to the investigator/research staff of the study.

The principal investigator may also screen the medical records of patients with whom they do not have a treatment relationship for the limited purpose of identifying patients who would be eligible to enroll in the study and to record appropriate contact information in order to approach these patients regarding the possibility of enrolling in the study.

During the initial conversation between the investigator/research staff and the patient, the patient may be asked to provide certain health information that is necessary to the recruitment and enrollment process. The investigator/research staff may also review portions of their medical records at MSKCC in order to further assess eligibility. They will use the information provided by the patient and/or medical record to confirm that the patient is eligible and to contact the patient regarding study enrollment. If the patient turns out to be ineligible for the research study, the research staff will destroy all information collected on the patient during the initial conversation and medical records review, except for any information that must be maintained for screening log purposes.

In most cases, the initial contact with the prospective subject will be conducted either by the treatment team, investigator or the research staff working in consultation with the treatment team. The recruitment process outlined presents no more than minimal risk to the privacy of the patients who are screened and minimal PHI will be maintained as part of a screening log. For these reasons, we seek a (partial) limited waiver of authorization for the purposes of (1) reviewing medical records to identify potential research subjects and obtain information relevant to the enrollment process; (2) conversing with patients regarding possible enrollment; (3) handling of PHI contained within those records and provided by the potential subjects; and (4) maintaining information in a screening log of patients approached (if applicable).

8.1 PRETREATMENT EVALUATION

- Within 28 days prior to study registration:

- Evaluation by Radiation Oncology
- Evaluation by Medical Oncology
- PET-CT +/- MR performed at MSKCC
- Complete Blood Count
- Comprehensive Metabolic Panel with Magnesium
- Serum Pregnancy Test for Women of Child Bearing Potential
- Biopsy of target tumor

- After study registration but before cisplatin weekly dose #1:
 - PET-CT +/- MR (only if imaging was not done prior to study registration or not done at MSKCC)
 - Biopsy of target tumor (if not completed prior to registration)
 - Peripheral blood sample for immunologic correlate studies, ctDNA, and/or BRCA mutation status (if unknown prior to study registration).

9.0 TREATMENT/ INTERVENTION PLAN

During radiation therapy, patients will undergo a physical exam and evaluation by a radiation oncologist once a week for toxicities in a status check visit as per current standard practice.

While receiving cisplatin, patients will be followed by a medical oncologist, who will obtain complete blood count once a week and serum chemistries with Mg²⁺ on D15 (± 3 days) of every cycle of cisplatin therapy. The medical oncologist will evaluate the patient on D1 of every cycle of cisplatin therapy. The length of one cycle of Cisplatin is 21 days.

Following the completion of RT, pending no toxicities, but prior to the week 12 post RT evaluable timepoint, patients will continue to receive cisplatin or until POD, based on MD discretion.

At Week 12 (12 ± 2 weeks after completion of radiation therapy), patients will be seen either by a radiation oncologist or a medical oncologist, and then every 6 months for routine follow-up visits either by a radiation oncologist or medical oncologist, until removal from study or death. Peripheral bloods and blood banking research samples (ctDNA) be collected at baseline, at the end of RT and at the 12 ± 2 week assessment point. Follow-up imaging studies (PET-CT +/- MRI) will be obtained at 12 ± 2 weeks after RT. PET/CT +/- MRI of the target lesion q6 months afterwards will be recommended but not required.

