13.0 CRITERIA FOR REMOVAL FROM STUDY

Participants will be removed from the protocol for any of the following reasons:

- Development of disease progression that warrants a change in the radiation or chemotherapy treatment plan or an alternative therapy.
- Any grade 4 non-hematologic toxicity, except in cases where the treating physician believes the patient is deriving benefit from remaining on the study.
- Chemotherapy treatment delay of 3 consecutive weeks for any reason
Note: Disruption to the cisplatin treatment schedule for 3 weeks due to unforeseen circumstances, holidays or the patient being on vacation is permitted and will be reviewed on a case-by-case basis.
- For safety reasons, the investigator considers it to be in the best interest of the participant that they be withdrawn
- The patient wishes to withdraw from the study
- HRR status is unable to be obtained from the core biopsy taken at the beginning of the study.

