However, we will plan to accrue a total of **62** patients in order to allow for early dropout due to disease progression/death prior to response evaluation, or inability to obtain HRR status from the core biopsy. For the primary analysis, all patients for whom HRR status can be ascertained will be included in the denominator. Patients who progress or die prior to the response evaluation at 12 +/- 2 weeks post-RT will be included as failures. This includes patients with disease progression outside of the irradiated tumor. Patients for whom HRR status cannot be ascertained or who left the study for nondisease related reasons will be replaced.

A secondary analysis of interest is to evaluate the CR rate among the subset of patients who are able to complete the planned study treatment and have a scan at the 12 +/- 2 week post-RT time point. Radiographic complete response (CR) of the irradiated tumor will be counted as a positive response to treatment. Radiographic response less than a CR, progression of the irradiated tumor or appearance of a new lesion within the radiated field will be categorized as a failure to respond to treatment. All other sites of metastatic disease that is outside of the irradiated field will be monitored and counted toward disease progression.

Based on prior experience with the HRR assay, we estimate that approximately 10% of patients will either 1) not have a definitive HRR status, or 2) will not complete the planned study treatment or 3) not have a response assessment at 12-14 week time point. To ensure we have 80% power for both the primary and secondary analyses we have added 8 patients to the sample size for a total of 62. The accrual number has been adjusted to 54 patients.

We expect to accrue 1 to 2 patients per month, or approximately 18 patients per year. Thus, accrual for the trial will be completed in 3.5 years. Based on previous data on the tolerability of cisplatin and radiation extrapolated from head and neck and gynecologic malignancies, we do not anticipate toxicities associated with the study treatment and as such, we have not incorporated an early stopping rule.

Secondary endpoints include overall response rates (CR+PR+stable disease), time to progression and CTCAE v4.0 toxicities. These endpoints will be compared by HRR status using the log-rank test for time-to-event endpoints and Fisher's exact test for binary endpoints.

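### The plan gives three ends of follow-up, so a patient removed for cisplatin delay, illness or toxicity may have no progression recorded inside the 24-week endpoint window

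*Combined protocol and SAP*

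**What the plan says.** **When follow-up ends.** Section 4.2 (Design) makes two statements in succession: "Patients will be followed up to 24 weeks after completion of RT to determine all study endpoints", and then "Clinical follow-up will continue until death". Section 9.0 describes the week-12 visit and the six-monthly visits after it, and ends them "until removal from study or death". Section 11.1 assesses toxicity to progression or death and does not mention removal.

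**When patients are removed.** Section 13.0 lists "Chemotherapy treatment delay of 3 consecutive weeks for any reason" and "Any grade 4 non-hematologic toxicity, except in cases where the treating physician believes the patient is deriving benefit from remaining on the study". A note allows a three-week disruption for unforeseen circumstances, holidays or vacation, reviewed case by case. Section 4.3.1 says of a three-week delay due to toxicity, "then the patient must discontinue protocol therapy and be removed from the study". It also removes patients when an intercurrent illness costs more than two weekly doses, and applies the three-week rule again to cisplatin given after radiotherapy.

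**How the endpoint is analysed.** Section 14.0: "Secondary endpoints include overall response rates (CR+PR+stable disease), time to progression and CTCAE v4.0 toxicities". The comparison by HRR status uses the "log-rank test for time-to-event endpoints". No start date, event definition, assessment schedule or censoring rule is given for time to progression. Section 14.0 also replaces patients who leave for reasons unrelated to disease, without saying whether their time-to-progression data are kept.

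**The concern.** A patient removed alive and without progression cannot be both followed to death (4.2) and released from visits at removal (9.0). The removal triggers are mostly treatment events rather than progression, and two of them carry exceptions that rest on judgement. The plan therefore merges three separate things: stopping protocol treatment, leaving study follow-up, and leaving the analysis.

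The secondary time-to-progression comparison is at stake. If sites follow 9.0, progressions after removal are not collected, and they may not be recoverable later. If those patients are then censored at removal, and stopping cisplatin is related to prognosis, the censoring is informative and the progression-free curve is too high. Even without bias, events are lost from a small comparison.

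**Working it through.** **1. The plan's own figure.** The only power figures are for the primary complete-response comparison: 85%, 83% and 80% at HRR-deficient shares of 40%, 35% and 30% (n = 54, one-sided 5%, 65% versus 30%). They reproduce with power = Φ(0.35/√(0.65·0.35/n₁ + 0.30·0.70/n₂) − 1.645). With 22/32 patients, √(0.01034 + 0.00656) = 0.130 and 0.35/0.130 = 2.69, so the power is Φ(1.05) = 85.2%. Groups of 19/35 and 16/38 give 83.3% and 80.1%. Nothing in this calculation depends on follow-up after removal. No power is stated for time to progression.

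**2. The passages side by side, for a patient removed alive and progression-free.**

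| Place | Follow-up after removal |
|---|---|
| 4.2, endpoints | to 24 weeks after radiotherapy |
| 4.2, clinical follow-up | to death |
| 9.0, visits | none |
| 11.1, toxicity | to progression or death |
| 14.0, time to progression | not stated; non-disease leavers are replaced |

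Inside the 24-week window, the only visit and scan required by 9.0 after radiotherapy is week 12 (± 2). The six-monthly visits and scans are optional in the section 10.0 table and first fall after 24 weeks. The conflict therefore matters for patients removed at or before week 12, who under 9.0 may miss that assessment.

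**3. Illustration of censoring at removal.** The documents give no removal rate for these reasons and no time-to-progression distribution. Assumptions:

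- Exponential time to progression with median 20 weeks: λ = ln 2/20 = 0.03466 per week.
- Horizon 29 weeks from first cisplatin: 2 weeks lead-in + 3 weeks radiotherapy + 24.
- A share p of patients scheduled for removal, uniform over weeks 5 to 17 (end of radiotherapy to week 12 after it).
- Hazard multiplied by k after removal.

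Censored at removal, Kaplan-Meier estimates exp(−29λ) = 0.366. The true proportion is 0.366 × [1 − p(1 − E)], where E is the mean of exp(−(k−1)λ(29−u)) over u from 5 to 17. E = 0.540 for k = 2 and 0.296 for k = 3. The overstatement is 0.366·p·(1 − E).

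| k | p | Overstatement (points) |
|---|---|---|
| 1 | any | 0 |
| 2 | 10% | 0.366 × 0.10 × 0.460 = 1.7 |
| 2 | 20% | 3.4 |
| 2 | 30% | 5.1 |
| 3 | 20% | 0.366 × 0.20 × 0.704 = 5.2 |

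For scale, at p = 20% and k = 2 the true proportion is 0.332, and its binomial standard error with 54 patients is √(0.332 × 0.668/54) = 6.4 points.

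**4. Events lost.** With k = 1, full follow-up gives 54 × (1 − 0.366) = 34.2 events. The chance of progressing before the scheduled removal is 1 − 0.688 = 0.312. At p = 20%, censoring at removal leaves 54 × (0.8 × 0.634 + 0.2 × 0.312) = 30.8 events, a loss of about 10%. With k = 2, events fall from 35.1 to 32.5 at p = 10% and from 36.1 to 30.8 at p = 20%.

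**5. A second set of assumptions.** Suppose the median is 4 months, removal is uniform over 0 to 4 months, 10–30% of patients have a removal time, and those patients carry 1.5 to 2 times the hazard throughout. Simulation then gives a Kaplan-Meier median too long by 0.07 months (3.90 versus 3.83, at 10% and 1.5 times) to 0.24 months (3.46 versus 3.22, at 30% and 2 times). With equal hazards the median is unbiased.

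**The case against.** **The clause in 9.0 has a narrow reach.** It covers the week-12 visit and the optional six-monthly visits, and only week 12 is both required and inside the endpoint window. This stands and limits the point to patients removed by then. But week 12 is the one required post-treatment scan, so losing it is not trivial.

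**Censoring is not stated.** A reader might infer that removed patients are censored for time to progression. No section says so. Section 14.0 names only a test, and its replacement sentence leaves dropping or replacing them equally possible. A reader might also infer from 4.2 that all later progressions count; its own preceding sentence limits endpoint determination to 24 weeks.

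**Patients without an HRR result.** Section 13.0 removes them, so they might seem to be part of the same problem. They cannot enter either group of a comparison by HRR status and are outside this point.

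**The illustration is pooled and assumed.** This stands. Section 14.0 expects about 10% of patients to lack an HRR result, not complete treatment or lack the week-12 assessment, all combined, so the 20–30% scenarios go beyond the plan's own expectation. If removal and its relation to progression are the same in both HRR groups, the log-rank test remains valid under the null. All patients get the same treatment, and section 5.3 restricts HRR results to the statistician and primary investigator. The documents give no evidence of differential removal. What remains at risk is the estimated curves and the number of events. The model also treats progression as continuously observed, which one required scan does not provide.

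**Conclusion.** The contradiction is real and in current text: follow-up ends at 24 weeks, at removal or at death, depending on the sentence read. Following 9.0 as written can discard progressions inside the 24-week window for a treatment-related reason, and section 14.0 does not say how such patients are analysed. The point should be corrected, but it concerns a secondary endpoint with no stated power.

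The size cannot be derived from the documents. Under the assumptions above, censoring at removal overstates the pooled progression-free proportion by about 2 to 5 points, less than one standard error in the scenarios shown. There is no bias if removal is unrelated to progression risk, although about 10% of events are still lost at 20% scheduled removal. It would go too far to conclude that the HRR comparison is biased, which would need removal to act differently in the two groups, or that the primary analysis is underpowered for this reason.

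**What to change.** - **Sections 4.2, 4.3.1, 9.0 and 13.0:** reconcile them so that stopping protocol treatment for delay, illness or toxicity does not end study follow-up. The rules for when treatment stops stay as the protocol has them.
- **Section 9.0:** follow patients, including the week-12 visit and scan, until death or withdrawal of consent, whether or not protocol treatment has stopped.
- **Section 14.0:** state that stopping protocol treatment does not by itself censor time to progression, and that progression is counted over the 24-week endpoint window. Give the start date, event definition, assessment schedule and censoring rule.
- **Replacement rule (14.0):** say how patients who stop treatment but stay in follow-up are handled. Rewording removal changes who counts as having left the study and is replaced, so without this sentence the primary analysis set could shift unintentionally.

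The cost is wording plus a small amount of extra data collection on patients off protocol treatment; section 4.2 already promises clinical follow-up to death. Because scans after week 12 stay optional, the change protects the week-12 assessment but does not guarantee a dated progression for every patient. It should be made prospectively.
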